## 4.2.2 Secondary Efficacy Analysis

### ▪ **Change in Leeds Dyspepsia Questionnaire (LDQ) Severity Score between baseline and week 4**

The actual values and change in values from baseline in Leeds Dyspepsia Questionnaire (LDQ) severity score will be summarized using the number of non-missing observations (n), mean, standard deviation (SD), median, minimum (Min) and maximum (Max) by Test group and Active Control group for baseline and week 8.

The endpoint will be analyzed by using analysis of covariance (ANCOVA) model. The model will include change in the LDQ score as dependent variable and treatment group, site and LDQ baseline values as covariates. Two-sided 95% confidence intervals will be constructed for the least square mean (LS Mean) differences between Test group and Active Control group.

The above analysis will be performed for Full Analysis (FA) subject sample.

### ▪ **Disease Specific Quality of Life (Nepean Dyspepsia Index NDI) assessed at baseline and week 8**

The Short Form Nepean Dyspepsia Index (SF-NDI) is composed of 10 QoL items investigating 5 domains. There are also an additional 15 items that measure frequency, intensity and bothersomeness. The symptom score can be modified to assess role functional dyspepsia score. The values of overall QoL score, QoL domain score, and functional dyspepsia score will be derived as per [section 5.3.2](#)

All 15 symptoms/items that measure frequency, intensity and bothersomeness will be summarized descriptively, using frequency count (n) and percentages by Test group and Active Control group for baseline and week 8.

All 15 symptoms/items will be converted to symptom scores by summing the values of frequency, intensity and bothersomeness for each symptom will be analyzed by using the number of non-missing observations (n), mean, standard deviation (SD), median, minimum (Min) and maximum (Max) by Test group and Active Control group for baseline and week 8.

Functional Dyspepsia score modified by specific symptom scores described in [section 5.3.2](#) will be analyzed by using the number of non-missing observations (n), mean, standard deviation (SD), median, minimum (Min) and maximum (Max) by Test group and Active Control group for baseline and week 8.

Each QoL domain/subscale raw scores and transformed scale scores as described in [section 5.3.2](#) and their overall scores will be summarized by using the number of non-missing observations (n), mean, standard deviation (SD), median, minimum (Min) and maximum (Max) by Test group and Active Control group for baseline and week 8.

A two sample t-test will be used to check the significance difference between Test group and Active Control group at 5% level of significance.

The above analysis will be performed for Full Analysis (FA) subject sample.

▪ **Change from baseline of NRS 11 score for symptoms after week 4 and week 8**

The patient is provided with the NRS 11 scale to mark changes for symptoms of sensation of bloating, early satiety, postprandial fullness, upper abdominal pain, or discomfort (epigastric pain, epigastric burning), anorexia (loss of appetite), heartburn, nausea, and vomiting.

The NRS scale scores for each symptom will be obtained as per [section 5.3.2](#).

The actual scores and change in scores from baseline for each symptom will be summarized using the number of non-missing observations (n), mean, standard deviation (SD), median, minimum (Min) and maximum (Max) by Test group and Active Control group for baseline and week 8.

The change in symptoms score will be analyzed by using analysis of covariance (ANCOVA) model. The model will include change in Symptom Score as dependent variable and treatment group, site, and Symptom baseline score as covariates. Two-sided 95% confidence intervals will be constructed for the least square mean (LS Mean) differences between Test group and Active Control group.

The above analysis will be performed for Full Analysis (FA) subject sample.

▪ **Responder Analysis of Satisfactory relief assessed by LDQ and NRS 11**

Based on the LDQ score, at the end of the study treatment subjects will be categorized into responders and non-responders (refer section 5.3).

Number of responders and non-responders will be summarized descriptively by using frequency count (n) and percentages (%) by Test Arm and Active Control Arm.

To check the significant difference between two treatment arms a chi-square test will be used when the normal approximation to the binomial is valid. Otherwise, a Fisher's exact test will be used if >20% of expected cell counts are less than 5.

Similarly, based on the NRS11 score, study treatment subjects will be categorized into responders and non-responders for each symptom (refer [section 5.3.2](#)) and similar analysis specified above will be performed.

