
Change in the overall severity of functional dyspepsia between baseline and week 8, as measured by the Leeds Dyspepsia Questionnaire (LDQ) severity score
 
Secondary endpoint(s):
 
 
• Change in the overall severity of functional dyspepsia between baseline and week 4, as measured by the Leeds Dyspepsia Questionnaire (LDQ) severity score
 
• Disease Specific Quality of Life (Nepean Dyspepsia Index NDI) assessed at baseline and week 8
 
• Change from baseline of NRS 11 score for symptoms (sensation of bloating, early satiety, postprandial fullness, upper abdominal pain or discomfort (epigastric pain, epigastric burning), anorexia (loss of appetite), heartburn, nausea and vomiting) after 4 and 8 weeks of treatment
 
• Responder analysis for adequate/satisfactory relief as assessed by LDQ and/or NRS 11
 
• Treatment acceptance and ease of use assessed by subjects using 5-point Likert scale
 
 
Safety:
 
 
• To evaluate the safety and tolerability of the two treatments by assessing the following safety endpoints: Treatment emergent adverse events (TEAEs) as detected by physical examination, laboratory assessments and vital signs.
 
		

Statistical Methods:
 
Efficacy
 
Primary efficacy:
 
 
• An ANCOVA analysis will be performed with the change in the LDQ score as dependent variable and treatment group, site and LDQ baseline value as additional factors. The difference between the two treatment groups will be calculated for the non-inferiority comparisons, together with a two-sided 95% confidence interval. Non-inferiority will be considered achieved if the lower bound of the 95% confidence interval of the difference between the two groups is greater than 1.75 (NI-margin). Normal approximation will be assumed for the parametric analyses. The primary analysis will be performed for both the per protocol set and the full analysis set. The analysis for the per-protocol set will be regarded as primary.
 
		

Name of Sponsor: Abbott	Name of Finished Product: Itopride Hydrochloride 150mg extended release tablets	Name of Active Ingredient(s): Itopride

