### **Quality of Life assessment using Short Form - Nepean Dyspepsia Index (SF-NDI)**

- Quality of life is an important health outcome, which is frequently measured in various clinical and epidemiological studies. Disease can have various effects on quality of life, it depends on the area of the body afflicted and how significant that area is to the individual.
- So, evaluating items by the individual patient according to their relative importance may be helpful and beneficial. This could be a more accurate method for evaluating how a disease affects the quality of life.
- The Short Form Nepean Dyspepsia Index (SF-NDI) was designed to evaluate the impairment in each component of a subject's life as wander ability to participate and enjoy these aspects of their lives.
- Short Form Nepean Dyspepsia Index (SF-NDI) Questionnaire will be used to measure the disease-specific Quality of Life of each participant of both arms (Test and Control Arm) at baseline (visit 2) and week 8 (visit 4).

[figure not shown]

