#### Secondary efficacy:

- Full analysis sample will be used for the analysis of the secondary endpoints.
- All secondary efficacy variables will be assessed using descriptive statistics.
- In addition, the change from baseline in LDQ score at week 4 and the NRS 11 score for each symptom will be evaluated using the same analysis as specified for the primary endpoint.
- Impact of rescue medication on efficacy and safety will be investigated by appropriate statistical methods like e.g. imputation methods depending on the number of subjects needing rescue medication. In addition subgroup analyses will be performed as well

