*All 4 symptoms (i.e., Pain or ache in upper abdomen, Burning sensation in upper abdomen PDS, Inability to finish a regular meal, Fullness after eating or slow digestion used) are to be included. " ----" refers to continuation of symptoms.*

*Repeat similar table for **Table 10.1.2.2.3: Summary of Functional Dyspepsia Score Assessed by Short Form Nepean Dyspepsia Index (SF-NDI) Questionnaire (by Age Group)***

*Repeat similar table for **Table 10.1.2.2.4: Summary of Functional Dyspepsia Score Assessed by Short Form Nepean Dyspepsia Index (SF-NDI) Questionnaire (by Geographical Region)***

**Table 10.1.2.2.3.1: Summary of Raw Score of Quality of Life (QoL) Assessed by Nepean Dyspepsia Index (SF-NDI) Questionnaire**

FULL ANALYSIS SUBJECT SAMPLE

Characteristics	Visit	Statistics	
 (N=xxx)	
 (N=xxx)
Overall QoL Score	Baseline	n	xxx	xxx
		Mean (SD)	xx.x (x.x)	xx.x (x.x)
		Median	xx.x	xx.x
		Min/Max	xx/xx	xx/xx
		p-value	x.xxx	
	Week 8	n	xxx	xxx
		Mean (SD)	xx.x (x.x)	xx.x (x.x)
		Median	xx.x	xx.x
		Min/Max	xx/xx	xx/xx
		p-value	x.xxx	
Domains: Tension	Baseline	n	xxx	xxx
		Mean (SD)	xx.x (x.x)	xx.x (x.x)
		Median	xx.x	xx.x
		Min/Max	xx/xx	xx/xx
	Week 8	n	xxx	xxx
		Mean (SD)	xx.x (x.x)	xx.x (x.x)

Interference With Daily Activities	Baseline	Median	xx.x	xx.x
		Min/Max	xx/xx	xx/xx
		p-value	x.xxx	
		n	xxx	xxx
		Mean (SD)	xx.x (x.x)	xx.x (x.x)
	Week 8	Median	xx.x	xx.x
		Min/Max	xx/xx	xx/xx
		p-value	x.xxx	
		n	xxx	xxx
		Mean (SD)	xx.x (x.x)	xx.x (x.x)
Eating/Drinking	Baseline	Median	xx.x	xx.x
		Min/Max	xx/xx	xx/xx
		p-value	x.xxx	
		n	xxx	xxx
		Mean (SD)	xx.x (x.x)	xx.x (x.x)
	Week 8	Median	xx.x	xx.x
		Min/Max	xx/xx	xx/xx
		p-value	x.xxx	
		n	xxx	xxx
		Mean (SD)	xx.x (x.x)	xx.x (x.x)

		p-value	x.xxx	
Knowledge/Control	Baseline	n	xxx	xxx
		Mean (SD)	xx.x (x.x)	xx.x (x.x)
		Median	xx.x	xx.x
		Min/Max	xx/xx	xx/xx
		p-value	x.xxx	
	Week 8	n	xxx	xxx
		Mean (SD)	xx.x (x.x)	xx.x (x.x)
		Median	xx.x	xx.x
		Min/Max	xx/xx	xx/xx
		p-value	x.xxx	
Work/Study	Baseline	n	xxx	xxx
		Mean (SD)	xx.x (x.x)	xx.x (x.x)
		Median	xx.x	xx.x
		Min/Max	xx/xx	xx/xx
		p-value	x.xxx	
	Week 8	n	xxx	xxx
		Mean (SD)	xx.x (x.x)	xx.x (x.x)
		Median	xx.x	xx.x
		Min/Max	xx/xx	xx/xx
		p-value	x.xxx	

Note 1: Baseline is defined as the last available observation prior to the first study drug administration.

Note 2: P-value is calculated by using two sample t-test at 5% level of significance.

Source: LXX00X.sas, <CRO>.Run DDMMYYYY HH:MM  
Abbott Protocol CCCC-xxx-yyyy

Page x/y

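### SF-NDI quality of life is compared by an unadjusted t-test with no difference or confidence interval, although baseline SF-NDI is collected and the SAP already has a suitable ANCOVA

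*SAP*

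**What the plan says.** - **Endpoint.** The protocol synopsis lists as a secondary endpoint "Disease Specific Quality of Life (Nepean Dyspepsia Index NDI) assessed at baseline and week 8". Protocol 8.1 and the flow chart in 8.6 place SF-NDI at visit 2 and visit 4, so every randomised subject should have a baseline value.
- **Protocol analysis.** Protocol 10.2, under Secondary efficacy, says "All secondary efficacy variables will be assessed using descriptive statistics". It then adds the primary-endpoint ANCOVA for LDQ at week 4 and for NRS 11, but not for SF-NDI.
- **SAP analysis.** SAP 4.2.2 summarises the SF-NDI scores by arm at baseline and week 8 (n, mean, SD, median, minimum, maximum) and then adds: "A two sample t-test will be used to check the significance difference between Test group and Active Control group at 5% level of significance". The sentence names neither a visit nor a variable.
- **Shells.** These fill the gap. The raw and transformed QoL tables carry the footnote "P-value is calculated by using two sample t-test at 5% level of significance". They show a p-value row at week 8 for the overall score and each domain, and at baseline for the overall score and every domain except Tension. They have no row for change from baseline, between-arm difference or confidence interval.
- **Neighbouring endpoint.** For NRS 11, in the same SAP section: "The model will include change in Symptom Score as dependent variable and treatment group, site, and Symptom baseline score as covariates". Then: "Two-sided 95% confidence intervals will be constructed for the least square mean (LS Mean) differences between Test group and Active Control group". LDQ at weeks 4 and 8 is treated in the same way.

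**The concern.** Three things are lost, and none of them need be.

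1. **Precision.** The visit 2 score predicts the week 8 score to some degree. A t-test on week 8 means leaves that predictable variation in the error term.
2. **Estimation.** The QoL tables end in a p-value. In a trial designed to show that two regimens perform alike, failing to find a difference at the 5% level is not evidence that the arms are similar. The useful result is the size of the difference and its uncertainty.
3. **Meaning of the baseline tests.** Under randomisation any baseline difference is due to chance, so a baseline p-value says nothing about treatment.

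The SAP tables index marks Tables 10.1.2.2.3.1 and 10.1.2.2.3.5 for headline results, so these p-values will be prominent. SAP 4.7 also repeats the analysis by gender, age group and country, where arms are smaller and chance baseline imbalance is larger.

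**Working it through.** **Plan figure used for scale.** The documents give no sample size for SF-NDI. The only design figure is for LDQ (Protocol 10.7): margin 1.75, SD 7, one-sided 2.5%, power 80%, 253 per arm.
- Normal approximation: 2 × (1.960 + 0.842)² × 7² / 1.75² = 2 × 7.85 × 16 = 251.2, so 252.
- With the noncentral t, power is 79.98% at 252 and 80.14% at 253, which reproduces 253.
- Dropout: 253 / 0.90 = 281.1, so 282 per arm and 564 in total.

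The sample size is therefore not in question. I use 253 per arm below only to set a scale.

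**Precision.** Let r be the correlation between baseline and week 8 SF-NDI. The documents do not give r, so a range is assumed. With 1:1 randomisation,

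Var(baseline-adjusted difference) / Var(unadjusted week 8 difference) ≈ 1 − r².

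The CI width scales with √(1 − r²). The unadjusted 95% half-width, in SDs of the week 8 score, is 1.96 × √(2/253) = 0.174.

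| Assumed r | Variance factor 1 − r² | Variance cut | CI narrower by | Half-width (SD units) | 253 per arm is worth, unadjusted |
|---|---|---|---|---|---|
| 0.3 | 0.91 | 9% | 4.6% | 0.166 | 253/0.91 = 278 |
| 0.5 | 0.75 | 25% | 13.4% | 0.151 | 253/0.75 = 337 |
| 0.7 | 0.51 | 49% | 28.6% | 0.125 | 253/0.51 = 496 |

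The table leaves out any effect of adjusting for site. Whether the dependent variable is change or the week 8 score makes no difference to the treatment estimate once baseline is in the model.

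**How far a baseline imbalance carries over.** At 253 per arm, 95% of chance baseline differences lie within 0.174 SD. Only r times the imbalance is expected at week 8. At r = 0.5 that is at most 0.5 × 0.174 ≈ 0.09 SD.

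**Raw and transformed scales.** The SAP 5.3.2 formula for a domain is 100 − [(raw − 2)/8 × 100] = 125 − 12.5 × raw, which is linear in the raw score. Overall scores are means of the five domains, so they are linear too. A test or CI on one scale is therefore the same inference as on the other.

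**Direction.** The worked example beneath that formula leaves out the subtraction from 100. For its raw domain scores 7, 9, 7, 8, 7:
- Formula: 37.5, 12.5, 37.5, 25.0, 37.5, mean 30.0.
- Example as printed: 62.5, 87.5, 62.5, 75.0, 62.5, mean 70.0.

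Until the two agree, the sign of a between-arm difference on the transformed scale is ambiguous.

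**The case against.** The best defence is that the protocol never promised ANCOVA for SF-NDI. It plans descriptive statistics for secondary endpoints and reserves ANCOVA for LDQ week 4 and NRS 11. On that view the t-test is the surplus item, and deleting it would restore agreement with the protocol and remove the uninformative p-values. That is a legitimate minimum correction, and it shows that SAP 7.1 omits a departure the SAP has already made. But it leaves the reader with no better estimate, when one can be had from data and code already in place. Listing 12.2.6.3.2 already derives the change from baseline.

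Several stronger readings are tempting, and the documents do not support them:

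- **That the t-test is biased by baseline imbalance.** It is unbiased under randomisation. Only a fraction r of any imbalance is expected to carry over, and the loss is one of precision.
- **That no interval can be had at all.** The shells give n, mean and SD per arm at week 8, so a reader can build an unadjusted interval by hand. The baseline-adjusted one cannot be recovered.
- **That every other efficacy comparison is adjusted.** The Likert acceptance item is compared by t-test or Mann-Whitney test. It has no baseline to adjust for.
- **That the plan will read a non-significant QoL result as comparability.** The QoL objective is only to assess quality of life in the two arms, and study success in SAP 4.2.1 rests on LDQ.

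It is also fair to say that the upper end of the precision range has no support in the documents.

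**Conclusion.** The point holds as a no-cost improvement to a secondary analysis. The SAP compares SF-NDI QoL scores without using a baseline it collects, prints no difference or interval, tests most of the scores at baseline, and does this for an endpoint that the protocol treats descriptively. Its own method for LDQ and NRS 11 is better and is available.

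ANCOVA gains precision for any non-zero correlation. How much depends on r, which is an assumption: a CI narrower by about 5% at 0.3, 13% at 0.5 and 29% at 0.7.

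A reader might infer that the trial's main result is at risk, or that the new interval would allow a non-inferiority claim for quality of life. Neither follows. The primary conclusion does not use SF-NDI, and no SF-NDI margin is defined, so the interval supports estimation only.

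**What to change.** 1. In SAP 4.2.2, replace the t-test by the NRS 11 model: ANCOVA of change in SF-NDI overall and domain scores, with treatment, site and baseline SF-NDI.
2. In the QoL shells, replace the t-test p-value and its footnote with the LS mean difference (test minus active control) and its two-sided 95% CI. Choose one scale, raw or transformed, for inference and keep the other as descriptive summaries.
3. Reconcile the transformed-score formula in SAP 5.3.2 with its worked example, and state which direction means better quality of life.
4. Delete the baseline p-values where the shells show them (overall score and every domain except Tension).
5. Record in SAP 7.1 that SF-NDI receives an inferential analysis where the protocol planned descriptive statistics only.

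The cost is SAP wording, edited shells and reuse of the existing ANCOVA code. No new data are needed.

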## Exploratory analysis

### ▪ Treatment acceptance and ease of use assessed by using 5-point Likert Scale

The subject's response of treatment acceptance for each point i.e. 1-Not at all satisfied, 2-Slightly satisfied, 3-Neutral, 4-Very satisfied, 5-Extremely satisfied will be summarized descriptively, using frequency count (n) and percentages (%) by Test group and Active Control group at the end of the study treatment (i.e., at week 8).

A descriptive summary of treatment acceptance will also be provided using number of non-missing observation (n), median, minimum (Min) and maximum (Max) by Test group and Active Control.

To find the significant difference of acceptance and ease of use between Test group and Active Control group a two-sample t-test or Mann Whitney test will be used at 5% level of significance based the normality of the data.

Normality of the response of 5-point likert scale scores will be checked by using Q-Q Plot or KS test.

## 4.3 Safety analysis

The Safety subject sample will be used for the analysis of the safety data.

Descriptive statistics for all safety and tolerability data will be presented by the Test group and Active Control. Only the necessary tables as required for the study will be generated, as specified in section 9.3, which provides the list of required reports.

### Adverse Events:

An AE that starts during a unique treatment or that already exists before the start of that unique treatment but worsens during the treatment, will be considered as treatment emergent for that unique treatment.

For the definition of treatment emergent, the following unique treatments are distinguished by applicable study period:

- Itopride Hydrochloride 150 mg extended release tablets
- Itopride Hydrochloride 50 mg film coated tablets

AEs will be reported on a per-subject basis, i.e. counting subjects rather than events. This means that if a subject suffers the same AEs repeatedly during the applicable study period, the event will be counted only once for that period. Repeated events per subject will be summarized according to the following rule: if a subject suffered the same AE more than once, the event will be assigned the worst severity, the closest relationship to the study drug and the earliest starting date. Only treatment emergent AEs will be reported.

A table which include TEAEs that have an incidence  $\geq 3\%$  in any treatment arm will be produced as per standard TLF AET003. cut-point will be used as  $\geq 3\%$ , instead of  $\geq 5\%$ .

In the listings, however, all occurrences of the AEs will be presented. For each unique treatment, treatment emergent AEs will be summarized per primary SOC, per HLT by primary SOC and per PT by HLT and primary SOC. Severity and drug-event relationship of treatment emergent AEs are summarized separately. Refer section 3.6.1 of SAP module 2 for detailed analysis strategy of AEs.

#### Laboratory Data:

Laboratory variables for hematology and biochemistry, including changes from baseline will be summarized. A frequency table will be presented for markedly abnormal values. Markedly abnormality for hematology will be determined based on the standard criteria outlined in Table 3 of SAP module 2. Markedly abnormality for Biochemistry variables will be determined based on the standard criteria outlined in Table 2.

The criteria for non-specified variables are as follows:

Variable	SI Units		
	Unit	Lower Limit	Upper Limit
Random Blood Sugar	mmol/L	3.9	11.1
Serum Prolactin	mcg/L	--	0.1 (100ng/l)
Serum Lipase	U/L	--	420
Ionized Calcium	mmol/L	0.9	1.5

Blood differentials whose values are reported in %, the limits for markedly abnormal values that are as follows:

Variable	SI Units		
	Unit	Lower Limit	Upper Limit
Basophils	%	--	4
Eosinophils	%	--	5
Lymphocytes	%	--	40
Monocytes	%	--	10
Neutrophils	%	--	70

Shift tables will be presented according to the lab reference ranges (low, normal, or high). Refer section 3.6.2 of SAP Module 2 for detailed analysis strategy.

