#### **4.7 Subgroup Analysis**

Primary, secondary efficacy endpoints (LDQ at 4 and 8 weeks, NRS11 (different symptoms), responder rate, functional dyspepsia score by SF-NDI, raw and transformed scores by SF NDI), exploratory endpoint of treatment acceptance and safety endpoints (overall summary of AEs, prolactin levels and change from baseline in prolactin) will be analyzed across subgroups using the same analysis as specified for the primary, secondary and safety endpoints.

The subgroups are defined as follows:

Gender:

- Female
- Male

Age Group:

- $\geq 18$  to  $\leq 44$
- $\geq 45$  to  $\leq 59$
- $\geq 60$

Geographical region (Country):

- Armenia
- Malaysia
- Philippines
- Thailand
- Vietnam

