### 7.2 Changes from previous SAP Version

Sr. No.	Changes
1	Added General Considerations for the Analysis section
2	Included sample SAS code for Missing Values Imputation and for MMRM Model.
3	Summarized all 15 symptoms of SF-NDI as a score in addition to individual symptom's summaries
4	QoL domains are now summarized based on both raw scores and transformed scores; initially, only raw scores were provided. Derivation also added for transformed scores.
5	Updated AE table summarizing adverse events with incidence $\geq 3\%$ instead of incidence $\geq 5\%$
6	Elaborated the Safety Analysis section and added other analysis section specifying baseline tables, summaries, and listings.
7	Defined markedly abnormal ranges for non-standard variables of Hematology and Biochemistry.

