AET005	Adverse Events	10.1.3.1.4	Incidence of TEAEs With a Reasonable Possibility for a Causal Relationship (Investigator's Judgment) – Safety Subject Sample		NA	NA
AET006	Adverse Events	10.1.3.1.5	Incidence of TEAEs by Maximum Severity (Investigator's Judgment) – Safety Subject Sample		NA	NA
AET007	Adverse Events	10.1.3.1.6	Incidence of TESAEs – Safety Subject Sample		NA	NA
AET008	Adverse Events	10.1.3.1.7.1	Incidence of TEAEs Leading to Study Termination – Safety Subject Sample		NA	NA
AET009	Adverse Events	10.1.3.1.8	Incidence of non-serious TEAEs – Safety Subject Sample		NA	NA
AET010	Adverse Events	10.1.3.1.9	Incidence of non-serious TEAEs in $\geq 3\%$ of the Subjects in Any Treatment Group – Safety Subject Sample		NA	NA

Output Code	Clinical Domain	Output Number	Title	Produced for:		
				Headline Results	SMT	Interim Analysis
LBT001	Laboratory Tests	10.1.3.2.1.1	Summary of Quantitative Safety Laboratory Variables (Biochemistry)– Safety Subject Sample		NA	NA
LBT001	Laboratory Tests	10.1.3.2.1.2	Summary of Quantitative Safety Laboratory Variables (Hematology)– Safety Subject Sample		NA	NA
	Laboratory Tests	10.1.3.2.1.3	Summary of Quantitative Safety Laboratory Variable Serum Prolactin (by Gender) – Safety Subject Sample		NA	NA
	Laboratory Tests	10.1.3.2.1.4	Summary of Quantitative Safety Laboratory Variable Serum Prolactin (by Age Group) – Safety Subject Sample		NA	NA
	Laboratory Tests	10.1.3.2.1.5	Summary of Quantitative Safety Laboratory Variables Serum Prolactin (by Geographical Region) – Safety Subject Sample		NA	NA

Output Code	Clinical Domain	Output Number	Title	Produced for:		
				Headline Results	SMT	Interim Analysis
LBT003	Laboratory Tests	10.1.3.2.2.1	Shifts of Quantitative Safety Laboratory Variables from Baseline to Each Post-Baseline Visit Based on Reference Ranges (Biochemistry)– Safety Subject Sample		NA	NA
LBT003	Laboratory Tests	10.1.3.2.2.2	Shifts of Quantitative Safety Laboratory Variables from Baseline to Each Post-Baseline Visit Based on Reference Ranges (Hematology) – Safety Subject Sample		NA	NA
LBT004	Laboratory Tests	10.1.3.2.3.1	Incidence of Markedly Abnormal Safety Laboratory Variables (Biochemistry) – Safety Subject Sample		NA	NA
LBT004	Laboratory Tests	10.1.3.2.3.2	Incidence of Markedly Abnormal Safety Laboratory Variables (Hematology) – Safety Subject Sample		NA	NA

Output Code	Clinical Domain	Output Number	Title	Produced for:		
				Headline Results	SMT	Interim Analysis

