AEL010	Adverse Events	10.1.3.1.11	Listing of Other SAEs - All Subjects Consented Subject Sample			
AEL012	Adverse Events	12.2.7.3	Listing of TEAEs Leading to Discontinuation of Study Drug – Safety Subject Sample		NA	NA
AEL013	Adverse Events	8.3.2.1	Data Portion for Subject Narratives – All Subjects Consented Subject Sample		NA	NA
LBL003	Laboratory Data	12.2.8.1.1	Quantitative Safety Laboratory Variables (Biochemistry) - All Subject Consented Sample		NA	NA
LBL003	Laboratory Data	12.2.8.1.2	Quantitative Safety Laboratory Variables (Hematology) - All Subject Consented Sample		NA	NA

Output Code	Clinical Domain	Output Number	Title	Produced for:		
				Headline Results	SMT	Interim Analysis
LBL008	Laboratory Data	12.2.8.2.1	Markedly Abnormal and/or Clinically Significant Safety Laboratory Variables (Biochemistry)– Safety Subject Sample		NA	NA
LBL008	Laboratory Data	12.2.8.2.2	Markedly Abnormal and/or Clinically Significant Safety Laboratory Variables (Hematology) – Safety Subject Sample		NA	NA
LBL007	Laboratory Data	12.2.8.3	Reference Ranges - All Subject Consented Sample		NA	NA
VSL005	Vital Signs	12.2.8.4	Vital Signs - All Subject Allocated to Treatment Subject Sample		NA	NA
VSL004	Vital Signs	12.2.8.5	Markedly Abnormal Vital Signs – Safety Subject Sample		NA	NA

Note: The blank output code denotes a non-standard output.

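### The markedly abnormal limit for serum prolactin, 0.1 mcg/L, would probably flag nearly every subject, making that row of the safety table and that flag in the listing uninformative

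*SAP*

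**What the plan says.** SAP 4.3, Laboratory Data, takes most markedly abnormal criteria from Module 2 and adds its own for variables that Module 2 does not cover: "The criteria for non-specified variables are as follows". The prolactin row of that table reads "Serum Prolactin mcg/L -- 0.1 (100ng/l", and the lower limit is blank. SAP 7.2 lists these limits among the changes from the previous SAP version: "Defined markedly abnormal ranges for non-standard variables of Hematology and Biochemistry".

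The same section says how the limits are used: "A frequency table will be presented for markedly abnormal values". Two planned outputs apply them to biochemistry:

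- Table 10.1.3.2.3.1 in SAP 9.3.1: "Incidence of Markedly Abnormal Safety Laboratory Variables (Biochemistry) – Safety Subject Sample".
- Listing 12.2.8.2.1 in SAP 9.3.2: "Markedly Abnormal and/or Clinically Significant Safety Laboratory Variables (Biochemistry)– Safety Subject Sample".

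Prolactin is measured fasting (Protocol 8.2), at screening and at week 8 (Protocol 8.6, Table 2), in local laboratories (Protocol 16.3). SAP 4.7 names it among the "safety endpoints (overall summary of AEs, prolactin levels and change from baseline in prolactin") to be analysed by gender, age group and country. Neither document states a prolactin reference range or expected values.

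**The concern.** A markedly abnormal limit is useful only if ordinary values fall inside it and notable values fall outside. An upper limit of 0.1 mcg/L looks far below ordinary adult prolactin. If it is, the table would report almost everyone in both arms as markedly abnormal, whatever either formulation does. The listing would fill with ordinary values, among which the flag would not pick out a true outlier. A reader who took the incidence at face value would also be misled about safety. Prolactin is the only laboratory variable that SAP 4.7 singles out, so this row is likely to be read.

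**Working it through.** **1. Reproduce the stated limit.** The cell gives 0.1 mcg/L and, in brackets, 100 ng/L.

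- 0.1 mcg/L × 1000 ng/mcg = 100 ng/L.
- 100 ng/L ÷ 1000 mL/L = 0.1 ng/mL.

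The two forms agree. The conversion is right, and a wrong label in the unit column alone cannot explain the row. As written, a programmer would flag any value above 0.1 mcg/L.

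**2. Compare with ordinary values.** The documents give no range, so one is assumed: fasting adult prolactin anywhere from 1 to 25 mcg/L (1 mcg/L = 1 ng/mL).

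- 1 ÷ 0.1 = 10 times the limit.
- 5 ÷ 0.1 = 50 times.
- 25 ÷ 0.1 = 250 times.

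**3. Share of subjects flagged.** Assume log-normal prolactin with median m and log-scale standard deviation s. The share above a limit L is 1 − Φ((ln L − ln m)/s). With L = 0.1, m from 1 to 20 mcg/L and s from 0.4 to 0.8 (all assumed):

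| Median m (mcg/L) | s | Flagged | Flagged if every value doubles |
|---|---|---|---|
| 1 | 0.4 | 100.000% | 100.000% |
| 1 | 0.6 | 99.994% | 100.000% |
| 1 | 0.8 | 99.800% | 99.991% |
| 2 | 0.4, 0.6 | 100.000% | 100.000% |
| 2 | 0.8 | 99.991% | 100.000% |
| 5, 10, 20 | 0.4 to 0.8 | 100.000% | 100.000% |

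The least extreme case is m = 1, s = 0.8: (ln 0.1 − ln 1)/0.8 = −2.303/0.8 = −2.88, so 1 − Φ(−2.88) = 0.998. With all 282 planned subjects of an arm measured, that is 0.998 × 282 = 281.4 subjects flagged.

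**4. Can the flag respond to a rise?** In that same case a doubling of every value moves the flagged share by 99.991 − 99.800 = 0.19 percentage points. Everywhere else in the grid the movement is smaller. A difference between formulations of that size in prolactin would not be visible in the row.

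**5. How wrong would the assumption have to be?** Half the subjects escape the flag only if the median is 0.1 mcg/L or lower, which is 1 ÷ 0.1 = 10 times below the bottom of the assumed range.

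**The case against.** The strongest objection concerns scope. A reader might infer that the trial could not show a prolactin rise or a difference between formulations. The documents do not support that, because several planned outputs never use the 0.1 limit:

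- Biochemistry summaries with change from baseline (Table 10.1.3.2.1.1).
- Prolactin tables by gender, age group and region, whose shell in SAP 10.1 includes an LS mean difference with 95% confidence interval and p-value.
- Shift tables based on laboratory reference ranges (Table 10.1.3.2.2.1).
- Individual values in Listing 12.2.8.1.1, with reference ranges in Listing 12.2.8.3.
- The investigator's judgement of clinical significance (Protocol 8.2). By its title, Listing 12.2.8.2.1 also covers clinically significant values.

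This objection stands in full. For the same reason SAP 4.7 shows that prolactin matters, but not that its subgroup analysis is damaged: it names "prolactin levels and change from baseline in prolactin", and neither uses the limit.

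Three further objections stand in part:

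- **The prolactin range comes from outside the documents.** True, so the conclusion is conditional on it, but it holds at every point of the assumed range.
- **Module 2 is not among the documents.** It may add a condition to the definition, such as a required change from baseline, and it fixes the table's layout. With such a condition the share flagged could be well below 100%. That condition would then decide the flag, and a limit nearly everyone exceeds would add nothing. Whether the table reports baseline values also cannot be checked.
- **The cause is unknown.** A figure per mL read as per L would produce this row, since 100 ng/mL is 100 mcg/L, 1000 times the printed limit. That is one possibility; the documents do not show what was intended.

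**Conclusion.** The limit is wrong as written. On the assumption that ordinary fasting prolactin lies between 1 and 25 mcg/L, and that Module 2 adds no further condition, about 100% of subjects in both arms would be flagged (99.8% to 100% over the log-normal cases tried). A doubling of prolactin would move that figure by at most about 0.2 percentage points.

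The consequence is confined to the prolactin row of Table 10.1.3.2.3.1 and the markedly abnormal flag for prolactin in Listing 12.2.8.2.1. Both would be uninformative, and the table would mislead. The non-inferiority analysis and the other prolactin outputs are unaffected. The point still deserves correction before database lock, because the row would misreport a safety variable the SAP itself singles out.

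**What to change.** Before database lock the sponsor should:

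1. Confirm the intended prolactin limit and its unit.
2. Correct the prolactin row in SAP 4.3 and carry the change into the programming specification. Alternatively, define the flag as a stated multiple of the local laboratory's upper reference limit; reference ranges are already needed for the shift tables and Listing 12.2.8.3. The documents do not say whether those ranges are sex-specific, so this should be checked before relying on it.
3. State that local laboratory results are converted to one unit before the limit is applied.
4. Check the corrected row against any further condition in Module 2 section 3.6.2, to which SAP 4.3 refers for the laboratory analysis.

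The cost is one table cell, a sentence on units and the matching line of the programming specification. No data collection changes.
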